#### 6.1.10 GSK2141795 Dose Modification for Hypo- and Hyperglycemia

To reduce the risk of hyperglycemia, patients with abnormal fasting glucose values at screening will be excluded. In addition, patients with Type 1 diabetes will also be excluded; however, patients with Type 2 diabetes will be allowed if diagnosed  $\geq$ 6 months prior to enrollment, and if presenting with regular hemoglobin A1C (HbA1C)  $\leq$ 8% at screening. Patients will have glucose and insulin monitored during the study. If hyperglycemia is observed, supportive therapy will be provided according to standard medical practice. Treatment will be dose reduced or discontinued for clinically significant toxicity that cannot be adequately managed medically.

- (Mild) Fasting blood glucose > 150mg/dL (8.3 mmol/l)  
Monitor fasting and preprandial glucose.
- (Moderate to Severe) Fasting blood glucose < 70 mg/dL (3.9 mmol/l) OR any blood glucose > 250 mg/dl (13.9 mmol/l)  
Instruct subject to hold study drug(s) and notify investigator immediately. The investigator should discuss intervention and possible resumption of GSK2141795 with the study chair and CTEP sponsor

If a blood glucose > 250 mg/dL (13.9 mmol/l) is observed the subject should be monitored for ketoacidosis as clinically indicated. If subject has evidence of ketoacidosis, then treatment should be undertaken with awareness that the action of insulin or other antihyperglycemic agents (e.g. sulfonylureas, biguanides, etc.) may be substantially blocked by the action of the GSK2141795. The action of insulin or other antihyperglycemic agents should be restored as GSK2141795 is cleared. If an antihyperglycemic agent is administered, then the subject should be observed closely for rebound hypoglycemia as GSK2141795 is cleared. Intravenous insulin treatment is recommended.

#### 6.1.11 GSK2141795 Dose Modification for Mucositis

Mucositis has been observed as a dose-limiting toxicity of GSK2141795

Event Name	Mucositis	
Grade of Event	Management	Dose Modification
Grade 1-2	Encourage oral hygiene. Offer topical supportive anesthetics. Encourage adequate hydration.	No change in dose Hold until ≤ Grade 1. Resume at same dose level.
Grade 3-4	Above, plus systemic opiate administration as needed. Consider IV hydration and hospital admission as appropriate. Temporarily discontinue study drug(s) and discuss with GSK Medical Monitor.	Temporarily discontinue GSK2141795 and discuss with study monitor. Hold* until < Grade 2. Resume at one dose level lower.
*Patients requiring a delay of ≥ 28 days should go off protocol therapy. **Patients requiring > two dose reductions should go off protocol therapy.		

### 6.1.12 Trametinib and/or GSK2141795 Dose Modification for Neutropenia

Event Name	Neutropenia	
Grade of Event	Management	Dose Modification
Grade 1	No change in dose	No change in dose
Grade 2	No change in dose	No change in dose
Grade 3-4	Hold only for febrile neutropenia (single temperature of > 38.3C OR a sustained temperature of ≥ 38C for more then 1 hour) OR grade 4 neutropenia (ANC < 500/ul)	Hold until < Grade 2. GCSF therapy may be started at the discretion of the treating physician. The dose of study drug(s) may be maintained if neutropenia was the only study drug related toxicity requiring dose modification and GCSF treatments are continued. Otherwise decrease by one dose level.
*Patients requiring a delay of ≥ 28 days should go off protocol therapy. **Patients requiring > two dose reductions should go off protocol therapy.		

### 6.1.13 Trametinib and/or GSK2141795 Dose Modification for Thrombocytopenia

Event Name	Thrombocytopenia	
Grade of Event	Management	Dose Modification
Grade 1	No change in dose	No change in dose
Grade 2	No change in dose	No change in dose
Grade 3-4	Hold only for grade 3 (< 50,000/ul) with bleeding ≥ grade 2 OR grade 4 thrombocytopenia (< 25,000/ul)	Hold* until platelet count has recovered to 30,000/ul. For grade 4 thrombocytopenia resume at one dose level lower, if indicated.
*Patients requiring a delay of ≥ 28 days should go off protocol therapy. **Patients requiring > two dose reductions should go off protocol therapy.		

## 7 ADVERSE EVENTS: LIST AND REPORTING REQUIREMENTS

Adverse event (AE) monitoring and reporting is a routine part of every clinical trial. The following list of AEs (Section 7.1) and the characteristics of an observed AE (Section 7.2) will determine whether the event requires expedited reporting (via CTEP-AERS) **in addition** to routine reporting.

### 7.1 Comprehensive Adverse Events and Potential Risks List(s) (CAEPRs)

#### 7.1.1 CAEPRs for CTEP IND Agent

##### 7.1.1.1 CAEPR for Trametinib dimethyl sulfoxide (GSK1120212B, NSC 763093)

The Comprehensive Adverse Event and Potential Risks list (CAEPR) provides a single list of reported and/or potential adverse events (AE) associated with an agent using a uniform presentation of events by body system. In addition to the comprehensive list, a subset, the

Specific Protocol Exceptions to Expedited Reporting (SPEER), appears in a separate column and is identified with bold and italicized text. This subset of AEs (SPEER) is a list of events that are protocol specific exceptions to expedited reporting to NCI via CTEP-AERS (except as noted below). Refer to the 'CTEP, NCI Guidelines: Adverse Event Reporting Requirements' [http://ctep.cancer.gov/protocolDevelopment/electronic\\_applications/docs/aeguidelines.pdf](http://ctep.cancer.gov/protocolDevelopment/electronic_applications/docs/aeguidelines.pdf) for further clarification.

**NOTE:** Report AEs on the SPEER **ONLY IF** they exceed the grade noted in parentheses next to the AE in the SPEER. If this CAEPR is part of a combination protocol using multiple investigational agents and has an AE listed on different SPEERs, use the lower of the grades to determine if expedited reporting is required. *Frequency is provided based on 968 patients.* Below is the CAEPR for Trametinib dimethyl sulfoxide (GSK1120212B).

**Version 2.3, October 26, 2015**

Adverse Events with Possible Relationship to Trametinib dimethyl sulfoxide (GSK1120212B) (CTCAE 4.0 Term) [n= 968]			Specific Protocol Exceptions to Expedited Reporting (SPEER)
Likely (>20%)	Less Likely (<=20%)	Rare but Serious (<3%)	
BLOOD AND LYMPHATIC SYSTEM DISORDERS			
	Anemia		Anemia (Gr 2)
CARDIAC DISORDERS			
		Heart failure	
		Left ventricular systolic dysfunction	
	Sinus bradycardia		
EYE DISORDERS			
	Blurred vision		
	Dry eye		
		Eye disorders - Other (chorioretinopathy also known as retinal pigment epithelial detachment)	
		Eye disorders - Other (retinal vein occlusion)	
	Eye disorders - Other (visual disorders) 		
GASTROINTESTINAL DISORDERS			
	Abdominal pain		Abdominal pain (Gr 2)
	Constipation		Constipation (Gr 2)
Diarrhea			Diarrhea (Gr 3)
	Dry mouth		Dry mouth (Gr 2)
	Dyspepsia		Dyspepsia (Gr 2)
	Mucositis oral		Mucositis oral (Gr 2)
Nausea			Nausea (Gr 3)
	Vomiting		Vomiting (Gr 3)
GENERAL DISORDERS AND ADMINISTRATION SITE CONDITIONS			
	Chills		Chills (Gr 2)

Adverse Events with Possible Relationship to Trametinib dimethyl sulfoxide (GSK1120212B) (CTCAE 4.0 Term) [n= 968]			Specific Protocol Exceptions to Expedited Reporting (SPEER)
Likely (>20%)	Less Likely (<=20%)	Rare but Serious (<3%)	
	Edema face		
Fatigue			Fatigue (Gr 3)
	Fever		Fever (Gr 2)
IMMUNE SYSTEM DISORDERS			
	Allergic reaction 		
INFECTIONS AND INFESTATIONS			
	Paronychia		Paronychia (Gr 2)
	Skin infection		Skin infection (Gr 2)
INVESTIGATIONS			
	Alanine aminotransferase increased		Alanine aminotransferase increased (Gr 2)
	Alkaline phosphatase increased		Alkaline phosphatase increased (Gr 2)
	Aspartate aminotransferase increased		Aspartate aminotransferase increased (Gr 2)
	CPK increased		
	Ejection fraction decreased		
METABOLISM AND NUTRITION DISORDERS			
	Anorexia		Anorexia (Gr 2)
	Dehydration		Dehydration (Gr 3)
	Hypoalbuminemia		
	Hypomagnesemia		Hypomagnesemia (Gr 2)
	Hyponatremia		Hyponatremia (Gr 3)
MUSCULOSKELETAL AND CONNECTIVE TISSUE DISORDERS			
	Arthralgia		
	Back pain		Back pain (Gr 2)
		Musculoskeletal and connective tissue disorder - Other (rhabdomyolysis)	
	Pain in extremity		Pain in extremity (Gr 2)
NERVOUS SYSTEM DISORDERS			
	Dizziness		Dizziness (Gr 2)
	Headache		Headache (Gr 2)
RESPIRATORY, THORACIC AND MEDIASTINAL DISORDERS			
	Cough		Cough (Gr 2)
	Dyspnea		Dyspnea (Gr 2)
		Pneumonitis	
SKIN AND SUBCUTANEOUS TISSUE DISORDERS			
	Alopecia		Alopecia (Gr 2)
	Dry skin		Dry skin (Gr 2)
		Palmar-plantar erythrodysesthesia syndrome	
	Periorbital edema		

Adverse Events with Possible Relationship to Trametinib dimethyl sulfoxide (GSK1120212B) (CTCAE 4.0 Term) [n= 968]			Specific Protocol Exceptions to Expedited Reporting (SPEER)
Likely (>20%)	Less Likely (<=20%)	Rare but Serious (<3%)	
	Pruritus		Pruritus (Gr 2)
	Skin and subcutaneous tissue disorders - Other (folliculitis)		Skin and subcutaneous tissue disorders - Other (folliculitis) (Gr 2)
Skin and subcutaneous tissue disorders - Other (rash) 			Skin and subcutaneous tissue disorders – Other (rash) (Gr 3)
VASCULAR DISORDERS			
	Hypertension		Hypertension (Gr 2)
Vascular disorders - Other (edema) 			Vascular disorders - Other (edema) (Gr 2)
	Vascular disorders - Other (hemorrhage) 		

This table will be updated as the toxicity profile of the agent is revised. Updates will be distributed to all Principal Investigators at the time of revision. The current version can be obtained by contacting [[contact]](mailto:[contact]). Your name, the name of the investigator, the protocol and the agent should be included in the e-mail.

Visual disorders include visual disturbance that can be associated with retinal hemorrhage, corneal graft rejection, cyclitis, eye nevus, halo vision, intraocular pressure increased, macular edema, visual acuity reduced, and vitreous detachment.

Hypersensitivity (allergic reactions) may present with symptoms such as fever, rash, increased liver function tests, and visual disturbances.

Skin and subcutaneous tissue disorders - Other (rash) may include rash, rash acneiform, rosacea, erythematous rash, genital rash, rash macular, exfoliative rash, rash generalized, erythema, rash papular, seborrhoeic dermatitis, dermatitis psoriasiform, rash follicular, and skin fissures.

Edema includes edema, lymphedema, and edema limbs.

The majority of hemorrhage events were mild. Major events, defined as symptomatic bleeding in a critical area or organ (e.g., eye, GI hemorrhage, GU hemorrhage, respiratory hemorrhage), and fatal intracranial hemorrhages have been reported.

**Adverse events reported on Trametinib dimethyl sulfoxide (GSK1120212B) trials, but for which there is insufficient evidence to suggest that there was a reasonable possibility that Trametinib dimethyl sulfoxide (GSK1120212B) caused the adverse event:**

**BLOOD AND LYMPHATIC SYSTEM DISORDERS** - Disseminated intravascular coagulation; Febrile neutropenia; Leukocytosis

**CARDIAC DISORDERS** - Atrial fibrillation; Cardiac arrest; Myocardial infarction; Restrictive cardiomyopathy

**EYE DISORDERS** - Eye disorders - Other (corneal graft rejection); Eye disorders - Other (cyclitis); Eye disorders - Other (eye nevus); Eye disorders - Other (intraocular pressure

increased); Eye disorders - Other (iritis); Eye disorders - Other (vitreous detachment); Eyelid function disorder; Flashing lights; Floaters; Glaucoma; Papilledema; Photophobia  
**GASTROINTESTINAL DISORDERS** - Ascites; Colitis; Enterocolitis; Esophagitis; Gastric ulcer; Gastritis; Gastrointestinal disorders - Other (obstruction gastric); Gastrointestinal disorders - Other (oropharyngeal pain); Gastrointestinal disorders - Other (pneumatosis intestinalis); Gastrointestinal fistula; Pancreatitis; Small intestinal obstruction  
**GENERAL DISORDERS AND ADMINISTRATION SITE CONDITIONS** - Flu-like symptoms; General disorders and administration site conditions - Other (axillary pain); General disorders and administration site conditions - Other (pneumatosis); Pain  
**HEPATOBIILIARY DISORDERS** - Cholecystitis; Hepatic pain  
**INFECTIONS AND INFESTATIONS** - Biliary tract infection; Device related infection; Enterocolitis infectious; Infections and infestations - Other (abscess limb); Pharyngitis; Upper respiratory infection  
**INJURY, POISONING AND PROCEDURAL COMPLICATIONS** - Bruising  
**INVESTIGATIONS** - Blood bilirubin increased; Creatinine increased; Electrocardiogram QT corrected interval prolonged; GGT increased; Lipase increased; Platelet count decreased; Serum amylase increased  
**METABOLISM AND NUTRITION DISORDERS** - Hyperglycemia; Hyperkalemia; Hyperuricemia; Hypocalcemia; Hypoglycemia; Hypokalemia; Metabolism and nutrition disorders - Other (hyperphosphatemia)  
**MUSCULOSKELETAL AND CONNECTIVE TISSUE DISORDERS** - Musculoskeletal and connective tissue disorder - Other (compression fracture); Musculoskeletal and connective tissue disorder - Other (muscle spasm); Myalgia; Neck pain  
**NEOPLASMS BENIGN, MALIGNANT AND UNSPECIFIED (INCL CYSTS AND POLYPS)** - Neoplasms benign, malignant and unspecified (incl cysts and polyps) - Other (tumor hemorrhage); Tumor pain  
**NERVOUS SYSTEM DISORDERS** - Dysgeusia; Encephalopathy; Intracranial hemorrhage; Lethargy; Nervous system disorders - Other (diplopia); Seizure; Stroke; Syncope; Transient ischemic attacks  
**PSYCHIATRIC DISORDERS** - Anxiety; Confusion; Depression; Insomnia; Personality change  
**RENAL AND URINARY DISORDERS** - Acute kidney injury; Renal and urinary disorders - Other (dysuria); Urinary incontinence  
**REPRODUCTIVE SYSTEM AND BREAST DISORDERS** - Vaginal fistula  
**RESPIRATORY, THORACIC AND MEDIASTINAL DISORDERS** - Pleural effusion; Pneumothorax; Productive cough; Pulmonary hypertension; Respiratory failure; Sinus disorder  
**SKIN AND SUBCUTANEOUS TISSUE DISORDERS** - Bullous dermatitis; Photosensitivity; Skin and subcutaneous tissue disorders - Other (erythema nodosum); Skin ulceration; Urticaria  
**VASCULAR DISORDERS** - Hot flashes; Hypotension; Thromboembolic event (venous)

**Note:** Trametinib dimethyl sulfoxide (GSK1120212B) in combination with other agents could cause an exacerbation of any adverse event currently known to be caused by the other agent, or the combination may result in events never previously associated with either agent.

7.1.1.2 CAEPR for GSK2141795 (NSC 767034)

The Comprehensive Adverse Event and Potential Risks list (CAEPR) provides a single list of reported and/or potential adverse events (AE) associated with an agent using a uniform presentation of events by body system. In addition to the comprehensive list, a subset, the Specific Protocol Exceptions to Expedited Reporting (SPEER), appears in a separate column and is identified with bold and italicized text. This subset of AEs (SPEER) is a list of events that are protocol specific exceptions to expedited reporting to NCI via CTEP-AERS (except as noted below). Refer to the 'CTEP, NCI Guidelines: Adverse Event Reporting Requirements' [http://ctep.cancer.gov/protocolDevelopment/electronic\\_applications/docs/aeguidelines.pdf](http://ctep.cancer.gov/protocolDevelopment/electronic_applications/docs/aeguidelines.pdf) for further clarification. Frequency is provided based on 150 patients. Below is the CAEPR for GSK2141795.

NOTE: Report AEs on the SPEER ONLY IF they exceed the grade noted in parentheses next to the AE in the SPEER. If this CAEPR is part of a combination protocol using multiple investigational agents and has an AE listed on different SPEERs, use the lower of the grades to determine if expedited reporting is required.

Version 2.1, July 26, 2013

Adverse Events with Possible Relationship to GSK2141795 (CTCAE 4.0 Term) [n= 150]			Specific Protocol Exceptions to Expedited Reporting (SPEER)
Likely (>20%)	Less Likely (<=20%)	Rare but Serious (<3%)	
GASTROINTESTINAL DISORDERS			
Diarrhea			Diarrhea (Gr 2)
	Esophagitis		
	Gastrointestinal mucositis 		
Nausea			Nausea (Gr 2)
Vomiting			Vomiting (Gr 2)
GENERAL DISORDERS AND ADMINISTRATION SITE CONDITIONS			
Fatigue			Fatigue (Gr 2)
METABOLISM AND NUTRITION DISORDERS			
Anorexia			Anorexia (Gr 2)
	Hyperglycemia		Hyperglycemia (Gr 2)
	Hypoglycemia		
RESPIRATORY, THORACIC AND MEDIASTINAL DISORDERS			
	Respiratory mucositis 		
SKIN AND SUBCUTANEOUS TISSUE DISORDERS			
	Rash maculo-papular		

This table will be updated as the toxicity profile of the agent is revised. Updates will be distributed to all Principal Investigators at the time of revision. The current version can be obtained by contacting [[contact]](mailto:[contact]). Your name, the name of the investigator, the protocol and the agent should be included in the e-mail.

Gastrointestinal mucositis may include Anal mucositis, Mucositis oral, Rectal mucositis, or Small intestinal mucositis under the GASTROINTESTINAL DISORDERS SOC.

Respiratory mucositis may include Laryngeal mucositis, Pharyngeal mucositis, or Tracheal mucositis under the RESPIRATORY, THORACIC AND MEDIASTINAL DISORDERS SOC

**Also reported on GSK2141795 trials but with the relationship to GSK2141795 still undetermined:**

**BLOOD AND LYMPHATIC SYSTEM DISORDERS** - Leukocytosis

**CARDIAC DISORDERS** - Cardiac arrest, Left ventricular systolic dysfunction, Ventricular tachycardia

**GENERAL DISORDERS AND ADMINISTRATION SITE CONDITIONS** - Non-cardiac chest pain

**HEPATOBIILIARY DISORDERS** - Hepatic failure

**INFECTIONS AND INFESTATIONS** - Wound infection

**INVESTIGATIONS** - Alanine aminotransferase increased; Alkaline phosphatase increased; Aspartate aminotransferase increased; Ejection fraction decreased; GGT increased

**METABOLISM AND NUTRITION DISORDERS** - Hypokalemia; Hyponatremia, Hypophosphatemia

**NERVOUS SYSTEM DISORDERS** - Dysgeusia; Dysphasia

**RENAL AND URINARY DISORDERS** - Acute kidney injury

**VASCULAR DISORDERS** - Thromboembolic event

**Note:** GSK2141795 in combination with other agents could cause an exacerbation of any adverse event currently known to be caused by the other agent, or the combination may result in events never previously associated with either agent.

## 7.2 Adverse Event Characteristics

- **CTCAE term (AE description) and grade:** The descriptions and grading scales found in the revised NCI Common Terminology Criteria for Adverse Events (CTCAE) version 4.0 will be utilized for AE reporting. All appropriate treatment areas should have access to a copy of the CTCAE version 4.0. A copy of the CTCAE version 4.0 can be downloaded from the CTEP web site [http://ctep.cancer.gov/protocolDevelopment/electronic\\_applications/ctc.htm](http://ctep.cancer.gov/protocolDevelopment/electronic_applications/ctc.htm).
- For expedited reporting purposes only:
  - AEs for the agent that are ***bold and italicized*** in the CAEPR (*i.e.*, those listed in the SPEER column, Section 7.1.1) should be reported through CTEP-AERS only if the grade is above the grade provided in the SPEER.
- **Attribution** of the AE:
  - Definite – The AE *is clearly related* to the study treatment.
  - Probable – The AE *is likely related* to the study treatment.
  - Possible – The AE *may be related* to the study treatment.
  - Unlikely – The AE *is doubtfully related* to the study treatment.
  - Unrelated – The AE *is clearly NOT related* to the study treatment.

## 7.3 Expedited Adverse Event Reporting

- 7.3.1 Expedited AE reporting for this study must use CTEP-AERS (CTEP Adverse Event Reporting System), accessed via the CTEP Web site (<http://ctep.cancer.gov>). The reporting procedures to be followed are presented in the “NCI Guidelines for Investigators: Adverse Event Reporting Requirements for DCTD (CTEP and CIP) and DCP INDs and IDEs” which can be downloaded from the CTEP Web site (<http://ctep.cancer.gov>). These requirements are briefly outlined in the tables below (Section 7.3.3).

In the rare occurrence when Internet connectivity is lost, a 24-hour notification is to be made to CTEP by telephone at [contact]. Once Internet connectivity is restored, the 24-hour notification phoned in must be entered electronically into CTEP-AERS by the original submitter at the site.

- 7.3.2 CTEP-AERS is programmed for automatic electronic distribution of reports to the following individuals: Study Coordinator of the Lead Organization, Principal Investigator, and the local treating physician. Each site will submit the electronic version of the CTEP-AERS report to the PMH Phase II Consortium Central Office. Once review by the lead group coordinator has taken place the report will be forwarded to NCI. CTEP-AERS provides a copy feature for other e-mail recipients.

### 7.3.3 Expedited Reporting Guidelines

Use the NCI protocol number and the protocol-specific patient ID assigned during trial registration on all reports.

**Note: A death on study requires both routine and expedited reporting regardless of causality, unless as noted below. Attribution to treatment or other cause must be provided.**

Death due to progressive disease should be reported as **Grade 5 “Neoplasms benign, malignant and unspecified (incl cysts and polyps) - Other (Progressive Disease)”** under the system organ class (SOC) of the same name. Evidence that the death was a manifestation of underlying disease (*e.g.*, radiological changes suggesting tumor growth or progression: clinical deterioration associated with a disease process) should be submitted.

In order to ensure the timely fulfillment of both US and Canadian IND regulatory reporting requirements, all CTEP-AERS reports must be sent to the PMH Phase II Consortium Central Office within 3 working days from the date the event was known to the investigator.

- In the unlikely event that an adverse event occurs that does not meet the reporting requirements for CTEP-AERS, but does meet the definition of a Serious Adverse Event, an CTEP-AERS report must still be completed and sent to the Central Office within 3 working days of the event being known to the investigator. The event must be telephoned or e-mailed to Central Office within 1 working day.

- The PMH Phase II Consortium Central Office will be responsible for reporting to Canadian regulatory authorities all Serious Adverse Events that are both unexpected and related to study drug. The Central Office will notify all Investigators of all Serious Adverse Events that are reportable to regulatory authorities in Canada from this trial or from other clinical trials as reported to the Central Office by the NCI U.S.

Investigators must notify their local Research Ethics Boards (REB/IRBs), according to their guidelines, of all SAE reports from their centre and file the report in their regulatory study binder. In addition, all reports sent out to centres by the PMH Phase II Consortium Central Office must be sent to local REB/IRBs, according to their guidelines. Documentation from the REB/IRB of receipt of these reportable events must be kept on file in each institution's regulatory binder.

**Late Phase 2 and Phase 3 Studies: Expedited Reporting Requirements for Adverse Events that Occur on Studies under an IND/IDE within 30 Days of the Last Administration of the Investigational Agent/Intervention**

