**FDA REPORTING REQUIREMENTS FOR SERIOUS ADVERSE EVENTS (21 CFR Part 312)**

**NOTE:** Investigators **MUST** immediately report to the sponsor (NCI) **ANY** Serious Adverse Events, whether or not they are considered related to the investigational agent(s)/intervention (21 CFR 312.64)

An adverse event is considered serious if it results in **ANY** of the following outcomes:

- 1) Death
- 2) A life-threatening adverse event
- 3) An adverse event that results in inpatient hospitalization or prolongation of existing hospitalization for ≥ 24 hours
- 4) A persistent or significant incapacity or substantial disruption of the ability to conduct normal life functions
- 5) A congenital anomaly/birth defect.
- 6) Important Medical Events (IME) that may not result in death, be life threatening, or require hospitalization may be considered serious when, based upon medical judgment, they may jeopardize the patient or subject and may require medical or surgical intervention to prevent one of the outcomes listed in this definition. (FDA, 21 CFR 312.32; ICH E2A and ICH E6).

**ALL SERIOUS** adverse events that meet the above criteria **MUST** be immediately reported to the NCI via CTEP-AERS within the timeframes detailed in the table below.

Hospitalization	Grade 1 Timeframes	Grade 2 Timeframes	Grade 3 Timeframes	Grade 4 & 5 Timeframes
Resulting in Hospitalization ≥ 24 hrs	10 Calendar Days			24-Hour 5 Calendar Days
Not resulting in Hospitalization ≥ 24 hrs	Not required		10 Calendar Days	

**NOTE:** Protocol specific exceptions to expedited reporting of serious adverse events are found in the Specific Protocol Exceptions to Expedited Reporting (SPEER) portion of the CAEPR

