**Expedited AE reporting timelines are defined as:**

- “24-Hour; 5 Calendar Days” - The AE must initially be reported via CTEP-AERS within 24 hours of learning of the AE, followed by a complete expedited report within 5 calendar days of the initial 24-hour report.

- “10 Calendar Days” - A complete expedited report on the AE must be submitted within 10 calendar days of learning of the AE.

Serious adverse events that occur more than 30 days after the last administration of investigational agent/intervention and have an attribution of possible, probable, or definite require reporting as follows:

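### The stated reporting route and time limits do not ensure the 24-hour deadline for grade 4 and 5 serious adverse events

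*Combined protocol and SAP*

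**What the plan says.** Four parts of the protocol bear on how a serious grade 4 or 5 event reaches NCI.

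- **Route (Section 7.3.2).** "Each site will submit the electronic version of the CTEP-AERS report to the PMH Phase II Consortium Central Office". The next step is "Once review by the lead group coordinator has taken place the report will be forwarded to NCI". No time is set for the review, and no class of report is exempt from it.
- **Site limit (Section 7.3.3).** The rule is "all CTEP-AERS reports must be sent to the PMH Phase II Consortium Central Office within 3 working days", counted from when the investigator learns of the event. The sentence gives timely US and Canadian regulatory reporting as its purpose and makes no exception for grade 4 or 5.
- **Deadline (reporting table in 7.3.3 and the definitions below it).** Serious events must "be immediately reported to the NCI via CTEP-AERS within the timeframes detailed in the table below". For grades 4 and 5 the table gives the 24-hour / 5-calendar-day timeline, defined as: "The AE must initially be reported via CTEP-AERS within 24 hours of learning of the AE". A complete report follows within 5 calendar days of that initial report.
- **Multicenter rules (Appendix B).** Two routes are allowed: (1) the institution reports directly to CTEP and copies the Coordinating Center, or (2) it reports to the Coordinating Center, which reports to CTEP. Appendix B also requires the protocol to describe which route applies.

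**The concern.** The only limit set for the first leg, site to Central Office, is longer than the deadline for the whole journey. The second leg, review and forwarding, has no limit. A site that reads the 3-working-day sentence as the operative rule, which its stated purpose invites, would satisfy that sentence and still breach the 24-hour requirement in the same section. A site that files at once could also be late through no fault of its own if the initial notice has to wait for review.

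At stake is timely notice to the sponsor of deaths and life-threatening events. Endpoints, sample size and analysis are not affected. This is an internal inconsistency in the safety-reporting text.

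**Working it through.** No sample-size or error-rate formula applies. The check is calendar arithmetic on the protocol's own limits.

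**Inputs**
- Site to Central Office: at most 3 working days from awareness (7.3.3).
- Review before forwarding to NCI: no limit stated (7.3.2).
- Initial report, grades 4 and 5: 24 hours from awareness (definitions in 7.3.3).
- Complete report: 5 calendar days after the initial report, so day 1 + 5 = day 6 if the initial report is made at 24 hours.
- 10-calendar-day reports: day 10 from awareness.
- Assumptions: working days are Monday to Friday; time is counted in whole days; the holiday case assumes that the following Monday is a holiday.

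**Formulas.** Let d be the calendar days taken up by 3 working days.
- Hours past the 24-hour limit on arrival at the Central Office = 24d − 24.
- Days left for review and forwarding of the complete report = 6 − d.

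| Day event is learned | d | 24d − 24 (hours) | 6 − d (days) | With Monday holiday: d / hours / days left |
|---|---|---|---|---|
| Monday, Tuesday | 3 | 48 | 3 | 3 / 48 / 3 |
| Wednesday, Thursday, Friday | 5 | 96 | 1 | 6 / 120 / 0 |
| Saturday | 4 | 72 | 2 | 5 / 96 / 1 |
| Sunday | 3 | 48 | 3 | 4 / 72 / 2 |

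**Results**
1. *Initial notice.* A site using its full allowance is past 24 hours on every day of the week, by 48 to 96 hours (120 with the holiday), before review begins.
2. *Complete report.* If the initial notice was on time, 1 to 3 days remain for review and forwarding, or none in the worst holiday case. It can be on time, with little slack.
3. *10-calendar-day reports.* Days left are 10 − 5 = 5 to 10 − 3 = 7, or 10 − 6 = 4 in the worst holiday case. Here the 3-working-day limit and a review step are compatible with the deadline.

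**Prompt site.** If the site files at hour 0, the 24-hour limit is met only if review and forwarding finish within 24 hours. Nothing in Section 7.3 requires that, and it describes no weekend or holiday cover for the review. Section 4.2 says the Central Office closes on Canadian statutory holidays. It says so in the context of registration, so this is only an indication.

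**The case against.** The best case for the plan has four parts.

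- **Three working days is a maximum.** A site that files at once and gets same-day review meets 24 hours. This is correct. A reader might infer that the deadline cannot be met by following the stated route; the documents do not support that.
- **The 24-hour duty binds separately.** Section 7.3.3 tells investigators to report any serious event to NCI immediately and within the table's timeframes. A site that takes three working days over a serious grade 4 event therefore breaches that duty. A reader might infer that late reports could arise with every site in compliance. That does not hold when the fault is the site's own delay.
- **A direct notice may be intended.** Section 7.3.1 provides that, if the internet is down, the 24-hour notification is telephoned to CTEP and later entered in CTEP-AERS by the original submitter at the site. No Central Office review is mentioned. The review in 7.3.2 can then be read as applying to the complete report only. The reading is reasonable, but the outage provision covers a rare exception, and for normal operation 7.3.2 describes the route through the Central Office without limiting it to complete reports. Section 7.3.1 also refers to NCI guidelines for the full procedures; they are not in the documents, so they cannot settle the point here.
- **The 1-working-day call.** For serious events outside the CTEP-AERS criteria, 7.3.3 adds: "The event must be telephoned or e-mailed to Central Office within 1 working day". A reader might infer that less urgent events have been given the faster clock. The text does not bear that out. Those events have no 24-hour CTEP-AERS trigger, so the call can be read as filling a gap. The written report has the same 3 working days in both cases, and CTEP-AERS automatically distributes reports to the lead organization's study coordinator.

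These points narrow the concern but do not remove it. No sentence says that the initial notice bypasses review, and none bounds the review.

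**Conclusion.** The point holds as an internal inconsistency. The stated route and limits do not ensure the 24-hour deadline for serious grade 4 and 5 events. There are two ways to miss it: a site relies on the 3-working-day limit and arrives 48 to 96 hours late (120 with the assumed holiday), or a prompt site is delayed by a review with no time limit. The conflict is confined to the initial notice.

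The conclusion assumes that the route in 7.3.2 covers the initial notice, which is its plain wording but not stated expressly. If only the complete report was meant, the protocol should say so, and the same edit does that. The documents give no figure for how often a notice would be late, or for any effect on safety decisions, and none is claimed. The change should be made because it protects timely safety reporting at almost no cost.

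**What to change.** Reconcile Sections 7.3.1, 7.3.2 and 7.3.3 with Appendix B:

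1. For events on the 24-hour / 5-calendar-day timeline, state that the site files the initial notification directly in CTEP-AERS within 24 hours and copies the Central Office at the same time. This is the first route already listed in Appendix B.
2. State that this notification does not wait for coordinator review.
3. Limit the 3-working-day rule and the review before forwarding to complete reports and 10-calendar-day reports.
4. Set a maximum review time, and say that site time plus review time may not exceed the reporting deadline. This matters most for the complete report, where 3 working days across a Monday holiday already use all six days.

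The cost is a few sentences of protocol wording and one more recipient on the 24-hour notice. Design, endpoints and analysis are unchanged.
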